**Table 16-2 Specific renal alert criteria and actions**

Renal Event	Actions
Serum creatinine increase 25 – 49% compared to screening or baseline (whichever is higher)	Confirm 25% increase after 2-5 days. If creatinine does not increase to $\geq 50\%$ compared to screening or baseline, revert to original scheduled sampling schedule. Collect urinalysis. Follow up within 2-5 days thereafter.
Serum creatinine increase $\geq 50\%$ compared to screening or baseline (whichever is higher)	Confirm $> 50\%$ within 2-5 days after receipt of the abnormal value. If confirmation of abnormal value is not possible in this timeframe, study drug must be withheld until further evaluation is possible. Collect urinalysis. Consider drug interruption. Assess participant for other causes of increased serum creatinine including: starting an ACEI or ARB, starting a nonsteroidal anti-inflammatory, new onset hypovolemia and new onset low blood pressure. Consider participant hospitalization / specialized treatment.
New onset dipstick proteinuria, typically +3 or +4, with a protein-creatinine ratio (PCR) $\geq 1\text{g/g}$ or $\geq 90\text{ mg/mmol}$	Confirm value after 2-5 days. Collect urinalysis. Assess participant for other causes of increased urine protein including: urinary tract infection, diabetes, strenuous exercise. Consider drug interruption / discontinuation.

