#### **4.5 Risks and benefits**

Detailed descriptions of the expected safety, tolerability and efficacy characteristics of each of the proposed individual treatment arms can be found in [Section 17](#).

Commercially Confidential Information

---

Commercially Confidential Information

Based on CCI risk considerations, additional safety measures employed in NEXSCOT include, but are not limited to:

- The study employs safety management measures which are considered relevant and appropriate for this patient population and protocol to facilitate safe conduct of the study.
- The study will only be conducted by investigators who have broad experience with patients who have multiple metabolic and/or liver comorbidities.
- Patients with advanced liver disease, for example cirrhosis or more severe hepatitis, will not be enrolled.
- Patients with evidence of ECG abnormalities consistent with significant cardiovascular risk will not be enrolled.
- Participants will have a visit every two weeks during the first two months of treatment for safety assessments, including ECGs and laboratory tests. Halfway through the final month of treatment (Month 3), study staff will contact the participant by phone to inquire about tolerability and safety.
- This protocol pre-specifies both liver and renal events requiring intervention ([Section 16.1](#) and [Section 16.2](#), respectively).
- The study will be also monitored by an internal Safety Assessment Committee (SAC), which will provide an additional layer of oversight for safety events. For further details, please refer to [Section 10.2.1](#) and the standalone Safety Surveillance Plan (SSP).
- Appropriate eligibility criteria and specific dose modification and stopping rules are included in this protocol. The risk to subjects in this trial will be minimized by compliance with the eligibility criteria and study procedures, as well as close clinical monitoring.

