Women are considered post-menopausal if they have had 12 months of natural (spontaneous) amenorrhea with an appropriate clinical profile (e.g., age appropriate history of vasomotor symptoms). Women are considered not of child bearing potential if they are post-menopausal or have had surgical bilateral oophorectomy (with or without hysterectomy), total hysterectomy, or tubal ligation at least six weeks ago. In the case of oophorectomy alone, only when the reproductive status of the woman has been confirmed by follow up hormone level assessment is she considered not of child bearing potential.

13. Sexually active males will be excluded UNLESS they agree to use a condom during intercourse while taking study medication and for a duration equal to approximately 5 times the terminal half-life after stopping study medication, and should not father a child in this period. A condom is required to be used also by vasectomized men in order to prevent delivery of the drug via seminal fluid. In addition, male participants must not donate sperm for the time period specified above. If local regulations deviate from the contraception methods listed above to prevent pregnancy, local regulations apply and will be described in the ICF.
14. Current or history of significant alcohol consumption for a period of more than 3 consecutive months within 1 year prior to screening. Significant alcohol consumption is defined as  $\geq 21$  units of alcohol per week in males and  $\geq 14$  units of alcohol per week in

females; a unit of alcohol is equivalent to 8 grams pure ethanol, 12 ounce (355 mL) beer, 4 ounce (118 mL) glass of wine, or 1 ounce (30 mL) shot of hard liquor.

15. Inability to reliably quantify alcohol consumption based upon local study physician judgment.
16. History of ongoing drug abuse within the 12 months prior to dosing.
17. Prior or planned (during the study period) bariatric surgery (e.g., gastroplasty, roux-en-Y gastric bypass).
18. Type I diabetes or uncontrolled Type II diabetes (defined as HbA1c > 9% at baseline).
19. Evidence of severe acute or chronic renal insufficiency, such as participants with eGFR < 60 mL/min/1.73m^2.
20. Suspected or confirmed Gilbert's syndrome.
21. Evidence of hepatic decompensation or severe liver impairment or cirrhosis, as defined by the presence of any of the following abnormalities (reminder that all lab ranges below must be confirmed at both screening and baseline):
  - Serum albumin < 3.2 g/dL
  - INR > ULN

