Concomitant therapies 	X																		
Adverse events	As required																		
Serious adverse events	As required																		
Comments	As required																		
Study completion information																	X	X	

X Assessment to be recorded in the clinical database

S Assessment to be recorded in the source documentation only

NR Non-remote, i.e. this assessment may not be performed remotely (i.e., must be performed at the originally qualified facilities).

 For treatments with an extended half-life, EOS1 will be required as a standard, non-EOS post-treatment follow up visit, and EOS2 will serve as the EOS visit. For all other treatments, EOS1 will serve as the EOS visit.

 If a participant discontinues study treatment early, the participant should be scheduled for a subsequent visit at which time all assessments at the EOS1 visit should be performed. For treatments with an extended half-life, if a participant discontinues early after EOS1, then the participant should be scheduled for a subsequent visit at which time all assessments at the EOS2 visit should be performed.

 Assessments to be performed pre-dose.

 All participants must fast for at least 8 hours prior to administration of study treatment.

 Visit will be conducted via telephone only. Participants are not required to present to the study site for assessments.

 Informed consent must be provided by all participants before any screening procedures are performed. The DNA assessment is optional and requires a separate informed consent to be signed.

Commercially Confidential Information

 Standard laboratory assays to be used for screening.

8a COVID-19 test highly recommended to be completed within 1 week prior to first dosing, as defined in Exclusion Criterion #29.

 Serum pregnancy tests will be performed at Screening and EOS; urine tests may be used at other time points.

 A complete physical examination is required at Screening, Day 1, Day 85, and at the study completion visit. A focused physical examination can be performed at all other visits where a physical examination is required. Please see protocol [Section 8.4](#) for more details.

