 Body height only measured at Screening. Waist and hip circumference (for waist-to-hip ratio calculation) only measured at Baseline and Day 85. Blood pressure and pulse rate will be measured in a sitting position at all marked visits.

 Coagulation panel includes PT/INR and aPTT.

 Fasting glucose and insulin used for Homeostasis Model Assessment of Insulin Resistance (HOMA-IR) calculation. Fasting lipid panel includes total cholesterol, LDL, HDL, and triglycerides. Additional analyses of HDL and LDL sub-fractions, ApoC3, and lipoprotein(a) at these timepoints may be performed depending on the compound under investigation.

 Trough PK samples will be collected at all visits during the treatment period (Day 1 to Day 85). On Day 29 and Day 57, additional samples will be obtained as marked.

 Assessment is only to be performed at EOS if a participant discontinues study treatment and from the study early.

 Assessment may include (

CCI

Commercially Confidential Information

CRP,

CCI

ELF Test).

 ELF Test only.

Commercially Confidential Information

 For orally-administered study medications, participants will be provided with a supply to self-administer for 12 weeks (Day 2 to Day 84).

Study medication will be administered by study staff on marked visit days. Participants should bring all used and unused medications, and diaries, to each visit. For other types of study medications, such as injectable monoclonal antibodies, dose administration will be managed by study staff on marked visit days.

 Orally-administered study medications only.

 Optional assessment.

 If Fibroscan is unavailable, alternative technology to assess liver stiffness may be considered upon consultation with the sponsor.

 Assessment is only to be performed at this visit if a participant discontinues study treatment early on or after Week 8 for any reason and should be scheduled as closely to the last dose of treatment as possible.

 Assessment should be performed after eligibility is confirmed from all other screening/baseline assessments wherever possible. MRE is an optional

assessment. See Imaging Subject Scanning Guide for further instructions.

 VAS assessments for itching of the skin.

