Conditions that were already present at the time of informed consent should be recorded in medical history of the participant.

Adverse events (including lab abnormalities that constitute AEs) should be described using a diagnosis whenever possible, rather than individual underlying signs and symptoms.

Adverse event monitoring should be continued for at least 5 half-lives following the last dose of study treatment or until the final study visit, whichever is longer.

Once an adverse event is detected, it must be followed until its resolution or until it is judged to be permanent (e.g., continuing at the end of the study), and assessment must be made at each visit (or more frequently, if necessary) of any changes in severity, the suspected relationship to the interventions required to treat it, and the outcome.

Information about adverse drug reactions for the investigational drug can be found in the Investigator's Brochure (IB).

Abnormal laboratory values or test results constitute adverse events only if they fulfill at least one of the following criteria:

- they induce clinical signs or symptoms
- they are considered clinically significant
- they require therapy

Clinically significant abnormal laboratory values or test results must be identified through a review of values outside of normal ranges/clinically notable ranges, significant changes from baseline or the previous visit, or values which are considered to be non-typical in participants with the underlying disease.

Follow the instructions found in the SOM for data capture methodology regarding AE collection for participants that fail screening.

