Baseline normal or elevated values	Normal or elevated values	Present	Laboratory monitoring and causality evaluation c	Continue or Interrupt dosing as appropriate g

ALP = alkaline phosphatase; ALT = alanine aminotransferase; AST = aspartate aminotransferase; eCRF = electronic case report form; INR = international normalized ratio; PK = pharmacokinetics; ULN = upper limit of normal

a The required confirmatory measurement should be obtained within 48-72 hours after the laboratory results become available. If prompt evaluation is not possible, study drug should be interrupted immediately (date of last study drug dose must be recorded in the eCRF).

b Combination of clinical signs and symptoms of right upper quadrant pain or tenderness, worsening or new fatigue, anorexia, nausea, rash, vomiting, diarrhea, fever, pruritus, and/or eosinophilia (> 5%).

c Frequent hepatic laboratory testing and clinical assessments, including a thorough causality evaluation, should be performed every other week at minimum, in consultation with the sponsor, until resolution of clinical symptoms and/or stabilization of liver biochemistries to baseline levels or baseline grade of abnormality.

d The sponsor should be notified of laboratory abnormalities and any clinical symptoms, and participants should be closely monitored until resolution of clinical symptoms/stabilization of liver biochemistries to baseline levels or baseline grade of abnormality.

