## 16.2 Appendix 2: Renal safety monitoring

Recommended actions and follow-up assessments regarding renal function data are shown in [Table 16-2](#). If evaluation of a renal event reveals a reversible etiology not related to study drug, the study drug may be restarted as long as the period of interruption is less than 10 days.

Note that the day to day variability of a particular participant's serum creatinine is reflected in the different values measured at screening versus baseline. Because of this, the investigator should use the higher of these two values as the reference against which to compare on-treatment serum creatinines.

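### Table 16-2 row 1 returns a persisting 25-49% creatinine rise to routine sampling; read as a single pass, a rise first seen at Day 57 then has about 18-24 days on drug without a scheduled creatinine

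*Protocol*

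**What the plan says.** Protocol Section 16.2 introduces the renal rules with the words "Recommended actions and follow-up assessments regarding renal function data are shown in" Table 16-2. The reference value is the higher of the screening and baseline creatinine. Row 1 covers a rise of 25-49%. It asks for confirmation after 2-5 days and then, provided creatinine has not reached 50%, says to "revert to original scheduled sampling schedule. Collect urinalysis. Follow up within 2-5 days thereafter". Row 2 (50% or more) is where the search for other causes and the possibility of drug interruption first appear for creatinine.

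Section 4.5 describes two-weekly visits with laboratory tests in the first two months of treatment. It continues: "Halfway through the final month of treatment (Month 3), study staff will contact the participant by phone to inquire about tolerability and safety". Footnote 5 of Table 8-1 confirms that this contact yields no sample: "Visit will be conducted via telephone only. Participants are not required to present to the study site for assessments". For oral drugs, footnote 22 says "participants will be provided with a supply to self-administer for 12 weeks (Day 2 to Day 84"). Day 85 assessments are pre-dose (footnote 3).

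The liver appendix treats an alert with continued dosing differently. Under Table 16-1 footnote c, hepatic tests and clinical assessments "should be performed every other week at minimum, in consultation with the sponsor, until resolution of clinical symptoms and/or stabilization of liver biochemistries".

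**The concern.** Row 1 sets one condition for going back to the ordinary schedule: the rise is below 50%. A creatinine that is confirmed, unchanged and still 25-49% above reference meets it. While scheduled draws are 14 days apart, this matters little. After Day 57 the next scheduled draw is 28 days away, at the end of dosing.

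Row 2 needs a creatinine value to trigger it. If a rise crosses 50% after the last row 1 check, the first scheduled sample to show it is the Day 85 pre-dose sample. By then the take-home supply is used up and at most one visit-day dose remains, so an interruption prompted by that sample would come too late to protect the participant. Two further rules look to this table. Section 9.1.1 exempts renal events from the related Grade 3 discontinuation rule and refers to Section 16.2. Section 9.2.1 puts arms sharing the suspect drug on hold after two discontinuations for a renal event as defined there.

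Safety is the primary objective (Section 2), and Section 4.5 lists the pre-specified renal events among the safety measures. The core sections are meant to stay constant over as many as five cohorts (Sections 1.1 and 3), so the cell would also govern later combinations.

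**Working it through.** The plan states no figure to reproduce. The check is calendar arithmetic on nominal days.

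**Inputs**
- Creatinine is part of the chemistry panel (Table 8-3).
- On-treatment chemistry days after the first dose are 15, 29, 43, 57 and 85. The columns of Table 8-1 are shifted in the available text. The ten marks in the chemistry row fit screening, baseline and Days 1, 15, 29, 43, 57, 85, 113 and 141, and Section 4.5 and footnote 5 support this reading.
- Confirmation comes 2-5 days after the first raised value, and the follow-up 2-5 days after that (Table 16-2 row 1).
- Two reading assumptions: the follow-up, whose test is not named, is a creatinine; and row 1 is run once.

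**Formulas**, for a rise first seen on day *d*
- Confirmation: *d* + 2 to *d* + 5.
- Follow-up: *d* + 4 to *d* + 10.
- Gap: next scheduled chemistry day minus follow-up day.

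| First seen | Confirmation | Follow-up | Next scheduled | Gap (days) |
|---|---|---|---|---|
| Day 15 | 17-20 | 19-25 | 29 | 4-10 |
| Day 29 | 31-34 | 33-39 | 43 | 4-10 |
| Day 43 | 45-48 | 47-53 | 57 | 4-10 |
| Day 57 | 59-62 | 61-67 | 85 | 18-24 |

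For Day 57: 85 − 67 = 18 and 85 − 61 = 24. Of 84 treatment days this is 18/84 = 21% to 24/84 = 29%.

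**Comparator.** Without any alert the interval is 85 − 57 = 28 days for everyone. Row 1 shortens it but does not close it.

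**Sensitivity for a Day 57 rise**
- Each result takes 0-3 days before the next step (assumption): the follow-up falls on Days 61-73, and the gap is 85 − 73 = 12 to 85 − 61 = 24 days.
- The follow-up is not a creatinine: 85 − 62 = 23 to 85 − 59 = 26 days.
- A rise first seen earlier and still 25-49% at Day 57: 18-24 days if row 1 is run again at Day 57, 28 days if it is not.

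**With one creatinine at Day 71:** 71 − 67 = 4 to 71 − 61 = 10 days from follow-up to Day 71, then 85 − 71 = 14 days. The longest gap becomes 14 days.

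**The case against.** The strongest reply is that row 1 is ambiguous. If the Day 61-67 follow-up still shows a 25-49% rise, it could be read as a fresh trigger, with another confirmation and follow-up, and the gap would shrink or vanish. The instruction to revert to the original schedule favors the single pass, but the wording does not settle it. The 18-24 days are therefore one reading, and the text should be made to say which is meant.

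The second reply is that the protocol has other protections, and they count for much.
- Section 3 lets the investigator reduce or interrupt drug and begin close observation for significant laboratory abnormalities, and cites Section 16.2 as additional information.
- Section 9.1.1 requires discontinuation where there is a safety risk.
- Sections 4.5.1 and 14 allow extra safety tests.
- Section 8.4.1 makes repeats mandatory for laboratory adverse events.
- The Safety Assessment Committee reviews data at frequent intervals (Section 10.2.1).

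What they leave open follows from Section 10.1.1: "Abnormal laboratory values or test results constitute adverse events only if they fulfill at least one of the following criteria", namely symptoms, clinical significance or need for therapy. An asymptomatic rise judged not clinically significant falls outside the mandatory repeats.

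Third, a 25% rise is the lowest renal tier in a marker whose daily variability Section 16.2 itself stresses, while the liver thresholds are higher multiples. Lighter follow-up could be a proportionate choice. That weakens the liver comparison, but it does not explain why a rise confirmed twice should be followed less closely in month 3 than in months 1 and 2.

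A reader might infer more than the documents support:
- *That row 1 creates the gap.* It does not. The 28-day interval applies to all participants, and row 1 adds two checks within it.
- *That drug cannot be interrupted before Day 85.* It can, on the investigator's judgment. What is missing is a scheduled value that would trigger row 2.
- *That a rise taking eGFR below 60 breaches the protocol.* Criterion 19 in Section 5.2, "Evidence of severe acute or chronic renal insufficiency, such as participants with eGFR < 60", governs entry. It is not an on-treatment rule.

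**Conclusion.** The point holds as a cheap safety improvement to consider. Row 1 lets a confirmed, persisting 25-49% rise return to the original schedule. For a rise first seen at Day 57 this leaves about 18-24 nominal days on drug before the next scheduled creatinine, or about 12-24 with result turnaround. Rises first seen at Days 15, 29 or 43 have only 4-10 days.

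The figure rests on a single pass through row 1, a follow-up that includes creatinine, and nominal visit days. The clinical exposure is confined to asymptomatic rises judged not clinically significant, and the documents give no frequency for these. The Site Operations Manual (which holds the visit windows), the Safety Surveillance Plan and the redacted cohort-specific text were not available, and any of them may add renal sampling. Safety data are summarized descriptively, so no statistical inference changes.

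**What to change.** Keep the opening sentence of row 1, which asks for confirmation, and replace everything after it with:

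> Collect urinalysis. Repeat serum creatinine within 2-5 days thereafter. If creatinine is < 25% above reference, revert to the original sampling schedule. If it is still 25-49% above reference, repeat it at least every 14 days while on study drug (scheduled draws count; for a rise present at Day 57, add one at about Day 71) until it is < 25% or dosing ends. If any value is >= 50%, follow the next row.

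The present sentence on reverting has to go. A rule added after it would leave two conflicting conditions in one cell. The new text also names the follow-up test and settles whether row 1 repeats. The longest gap on drug becomes 14 days, and row 2 can be reached with about 14 days of dosing left.

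The cost is one table cell in the next amendment, and one extra creatinine at about Day 71 for each participant whose rise persists at Day 57. For that participant a telephone contact becomes a sampling visit, at the site or off-site. Section 8 allows off-site chemistry only in certain countries and sites. Before Day 57 scheduled draws are already 14 days apart, so nothing is added beyond the repeat check. The schedule is unchanged for everyone else.

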**Table 8-3 Safety-related Laboratory Assessments**

Test Category	Test Name
Hematology	Hematocrit, Hemoglobin (HGB), Ery. Mean Corpuscular Hemoglobin (MCH), Ery. Mean Corpuscular HGB Concentration (MCHC), Ery. Mean Corpuscular Volume (MCV), Platelets, Erythrocytes, Leukocytes, Erythrocyte Morphology, Differential (Basophils, Eosinophils, Lymphocytes, Monocytes, Neutrophils, Bands, Other)
Chemistry	Albumin, Alkaline phosphatase, ALT, AST, Gamma-glutamyl-transferase (GGT), Lactate dehydrogenase (LDH), Bicarbonate, Calcium, Magnesium, Phosphate, Chloride, Sodium, Potassium, Creatinine, Creatine kinase, Direct Bilirubin, Indirect Bilirubin, Total Bilirubin, Total Cholesterol, LDL Cholesterol, HDL Cholesterol, Total Protein, Triglycerides, Blood Urea Nitrogen (BUN) or Urea, Uric Acid, Amylase, Lipase, HbA1c, Glucose
Urinalysis	Microscopic Panel (Erythrocytes, Leukocytes, Casts, Crystals, Bacteria, Epithelial cells) Macroscopic Panel (Dipstick) (Color, Bilirubin, Blood, Glucose, Ketones, Leukocytes esterase, Nitrite, pH, Protein, Specific Gravity, Urobilinogen)
Coagulation	Prothrombin time (PT), International normalized ratio (INR), Activated partial thromboplastin time (aPTT)
Pregnancy Test	Serum / Urine pregnancy test

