## **9 Discontinuation and completion**

### **9.1 Discontinuation from study treatment and from study**

#### **9.1.1 Discontinuation from study treatment in individual participants**

Discontinuation of study treatment for a participant occurs when study treatment is permanently stopped for any reason (prior to the planned completion of study drug administration) and can be decided by either the participant or the investigator.

Study treatment must be discontinued under the following circumstances:

1. Participant decision
2. Pregnancy
3. Use of prohibited treatment(s)
4. Any situation in which study participation might result in a safety risk to the participant
5. The investigator believes that continuation would negatively impact the safety of the participant or the risk/benefit ratio of trial participation

6. Hypersensitivity (CTCAE Grade 2 or higher) reaction to study medication
7. An adverse event that is CTCAE Grade 4 or higher, regardless of whether the event is suspected to be related to study drug(s)
8. An adverse event that is CTCAE Grade 3 and suspected to be related to study drug(s) (apart from liver and renal events - see below)
  - If a liver or renal event occurs, follow guidelines outlined in [Section 16.1](#) and [Section 16.2](#), respectively, regarding discontinuation of study treatment
9. Any laboratory abnormalities that in the judgment of the investigator, taking into consideration the participant's overall status, prevents the participant from continuing participation in the study

If discontinuation of study treatment occurs, the investigator should make a reasonable effort to understand the primary reason for the participant's premature discontinuation of study treatment and record this information.

Participants who discontinue from study treatment agree to return for the end of treatment assessments (i.e., EOS1 or EOS2) indicated in the Assessment schedule ([Table 8-1](#); and refer to [Section 8](#)).

If the participant cannot or is unwilling to attend any visit(s), the study staff should maintain regular telephone contact with the participant, or with a person pre-designated by the participant. This telephone contact should preferably be done according to the study visit schedule.

After discontinuation from study treatment, at a minimum, in abbreviated visits, the following data should be collected at visits or via telephone/email contact:

- new / concomitant treatments
- adverse events/Serious Adverse Events

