### **9.2.1 Study stopping rules**

#### **Treatment arm stopping rules**

If any of the following events occur, all ongoing treatment arms sharing the same suspect drug(s) will be placed on hold to further enrollment, and no new participants may be dosed, however dosing of those without safety concerns may continue. In addition, a full review of all available clinical safety data and discussion with the investigators will take place.

- One participant on study drug experiences any adverse event that is CTCAE Grade 4 or higher that is suspected to be related to study drug(s)
- Two participants on study drug experience a similar adverse event that is a CTCAE Grade 3 or higher other than ALT elevation regardless of whether the events are suspected to be related to study drug(s)
- Two participants are discontinued due to a liver event as defined in [Section 16.1](#)
- Two participants are discontinued due to a renal event as defined in [Section 16.2](#)

- Two participants meet the same individual participant stopping rule 6, 7, or 8 ([Section 9.1.1](#))
- One participant experiences any adverse event that is CTCAE Grade 5 regardless of whether the event is suspected to be related to study drug(s)
- One participant experiences an SAE that is suspected to be related to study drug(s)
- The Principal Investigator and Sponsor consider that the number and/or severity of adverse events justify discontinuation of the suspect drug(s)
- The Sponsor unilaterally requests it

Safety reviews for treatment arm stopping will be conducted cooperatively between medically qualified representatives of the sponsor and investigator and a joint decision will be made. The treatment arm may resume following the safety review, if the investigator and sponsor agree it is safe to proceed.

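### The proteinuria alert in Protocol Table 16-2 pairs two PCR limits that are not equal: 1 g/g is 113 mg/mmol, and 90 mg/mmol is 0.80 g/g

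*Protocol*

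**What the plan says.** Protocol Section 16.2 introduces its table with "Recommended actions and follow-up assessments regarding renal function data are shown in" Table 16-2. The third row of that table is the proteinuria alert: "New onset dipstick proteinuria, typically +3 or +4, with a protein-creatinine ratio (PCR) $\geq 1\text{g/g}$ or $\geq 90\text{ mg/mmol". Its actions begin "Confirm value after 2-5 days. Collect urinalysis. Assess participant for other causes of increased urine protein" and end "Consider drug interruption / discontinuation". Confirmation is therefore something done after the alert, not part of its definition.

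Other rules rely on this section. Section 9.1.1, on stopping treatment in an individual, says "If a liver or renal event occurs, follow guidelines outlined in" Sections 16.1 and 16.2. Section 9.2.1 puts arms that share a suspect drug on hold when "Two participants are discontinued due to a renal event as defined in" Section 16.2.

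The routine laboratory list, Table 8-3 in Section 8.4.1, covers urine protein by dipstick only: "Macroscopic Panel (Dipstick) (Color, Bilirubin, Blood, Glucose, Ketones, Leukocytes esterase, Nitrite, pH, Protein, Specific Gravity, Urobilinogen". It names neither PCR nor a unit for it. Section 5 places laboratory reference ranges in a separate laboratory manual, which was not available for this review.

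**The concern.** One row gives two numerical limits for the same ratio, in two unit systems, joined by *or*. A reader would expect them to be one limit written twice, and they are not. The row does not say whether *or* links two units for one limit or two separate limits.

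What is at stake is whether the alert actions start for a given result: the repeat value, the urinalysis, the search for other causes, and the decision about interrupting or stopping the drug. Safety is the primary objective, every participant has a history of Type 2 diabetes (Section 5.1, criterion 3c), and Table 16-2 itself lists diabetes among the causes of raised urine protein. Section 1.1 says that Sections 1 to 16 stay constant through the platform, and Section 3 plans up to five cohorts, so the pair of limits would carry into every later arm.

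**Working it through.** **Inputs.** From Table 16-2: a limit of 1 g/g and a limit of 90 mg/mmol. The molar mass of creatinine is not in the documents. I take it from the formula C4H7N3O with standard atomic masses:

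4 × 12.011 + 7 × 1.008 + 3 × 14.007 + 15.999 = 113.12 g/mol

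So 1 mmol of creatinine weighs 113.12 mg.

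**Formula.** PCR in mg/mmol = PCR in g/g × 113.12.

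**The printed pair.**

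- 1 g/g × 113.12 = 113.1 mg/mmol; the table prints 90.
- 90 / 113.12 = 0.796 g/g; the table prints 1.
- Gap: 113.12 − 90 = 23.12 mg/mmol, or 1 − 0.7956 = 0.204 g/g.
- Relative gap: 23.12 / 113.12 = 20.4% below the g/g limit (equivalently 113.12 / 90 − 1 = 25.7% above the mg/mmol limit).

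The plan's pairing cannot be reproduced. It would need a molar mass of 90 g/mol.

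**Sensitivity to the molar mass.**

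| Molar mass (g/mol) | 1 g/g in mg/mmol | 90 mg/mmol in g/g |
|---|---|---|
| 113.0 | 113.0 | 0.796 |
| 113.12 | 113.1 | 0.796 |
| 113.2 | 113.2 | 0.795 |
| 100 (crude rounding) | 100.0 | 0.900 |

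Even the crude rounding does not give 90.

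**What each reading implies.**

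1. *One limit in two units.* Take a participant with new-onset dipstick proteinuria and a PCR of 0.90 g/g. In the other unit this is 0.90 × 113.12 = 101.8 mg/mmol. It is an alert when reported in mg/mmol (at least 90) and not when reported in g/g (below 1). The same holds for any PCR from 90 to below 113.1 mg/mmol, that is, 0.80 to below 1.0 g/g.
2. *Two alternative limits.* Any PCR of at least 1 g/g is at least 113.1 mg/mmol and so already exceeds 90. The 1 g/g limit never decides a case, and the working limit is 0.80 g/g.

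The number of participants who would fall in the band cannot be estimated from the documents.

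**The case against.** The strongest reply is that the row is a complete rule if taken literally: meeting either limit triggers the alert, and nobody is classified two ways. Elsewhere the protocol puts unit equivalents in parentheses, as for kilograms and pounds in Section 5.1 and ounces and millilitres in Section 5.2, whereas this row uses *or*. That gives some support to the literal reading but does not rescue the row, because one of its two limits would then have no function.

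Under the other reading, sites would differ only if PCR is reported in different units, and the documents show no such mix. That stands: with one common unit there is no difference between sites. Which limit applies would still depend on that unit.

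The consequences are also remote, and this stands too. The actions are recommendations, the drug action is only to be considered, and the trigger also needs new-onset dipstick proteinuria. Section 9.1.1 separately requires treatment to stop for "Any laboratory abnormalities that in the judgment of the investigator" prevent continued participation, whatever the PCR. The arm hold in Section 9.2.1 needs two participants actually discontinued for a renal event. No visible endpoint, analysis set or planned summary uses PCR.

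It can also be said that the discrepancy errs towards caution, since no PCR of 1 g/g or more is missed in either unit. That assumes 1 g/g was intended. If 90 mg/mmol was intended as one limit in two units, reporting in g/g would miss results from 0.80 to below 1.0 g/g.

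**Conclusion.** The row is wrong as written. The mg/mmol limit is 20.4% below the g/g limit (90 against 113.1 mg/mmol; 0.796 against 1 g/g), and neither reading makes both numbers useful. The mismatch itself is certain, since it rests only on the molar mass of creatinine. The unit-dependent alert is conditional: it arises only if the row means one limit in two units.

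Severity is minor. The figure sits in a safety definition that Sections 9.1.1 and 9.2.1 point to, but it starts recommended checks rather than mandatory discontinuation. It has no bearing on sample size or on the statistical analysis.

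**What to change.** Print one limit with its true equivalent in Table 16-2.

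- **Suggested default: ≥ 0.80 g/g (90 mg/mmol).** This keeps the more cautious limit, which the literal wording already implies. 0.80 × 113.12 = 90.5 mg/mmol, so the rounding left is 0.5 mg/mmol (0.6%). The cost is a few more repeat tests at any site now applying 1 g/g.
- **If the sponsor's safety group intended 1 g/g: ≥ 1 g/g (113 mg/mmol).** 113 / 113.12 = 0.9989 g/g, so the rounding left is 0.1 mg/mmol (0.1%). The cost is that results from 90 to below 113 mg/mmol no longer trigger the alert.

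The documents do not show which was meant, so the sponsor must choose. The edit is one table cell, but it lies in the core protocol and needs the approvals in Section 14.1. It can go into the next amendment, since that section already requires a substantial amendment for each new cohort.
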